## Objectives

The **objective/purpose** of this study is to investigate the effects of CBD on driving performance, psychological status (i.e., mood, sedation, drowsiness), and cognitive function in healthy adults aged 18-30 years. This is because CBD is widely sold and consumed and there is some evidence that it may be sedating; however, this has never been evaluated in healthy adults. The **primary outcome** of this study will be driving performance, quantified using measures strongly associated with collision risk, including number of lane departures, standard deviation of lateral position (i.e., weaving), brake reaction time, and collision occurrence. Driving performance will be assessed using a driving simulator. **Secondary outcomes** will be changes in well-validated measures of mental sedation and cognitive function which includes performance on the VAMS, SSS, TMT, DSST, PVT, SRT. The VAMS and SSS are Likert-type scales which assess mental and physical sedation and sleepiness, respectively, at that moment and time. VAMS consists of 16 questions, while SSS only consists of 1. These measures can be summed with higher scores equating to more sedation. The SSS will be summed with greater perceived sleepiness receiving a larger score, similar to the VAMS. The DSST measures psychomotor speed, attention and working memory by requiring participants to translate numbers into symbols; the test is scored by the degree of completion and accuracy over a timed 90 second period. The TMT measures executive function and consists of two parts; the first part requires participants to connect numbers in ascending order, while the second part requires individuals to connect numbers and letters in sequence. The test is scored by the time it takes to accurately complete each test. Increases in time correlate with greater impairment. PVT and SRT are tests given on a computer tablet. They both measure participants reactions to stimuli.

## Study Design & Methodology

This is a randomized, parallel-group, double-blind, exploratory two-arm trial to assess the effects of CBD on driving ability along with changes in psychological status (e.g., sedation) and cognitive function. Thus, the data will be collected prospectively. The methodology of the study is below.

**Study Design and Protocol Overview.** We propose a randomized, parallel-group, double-blind, exploratory two-arm trial to assess the effects of CBD on driving ability along with changes in psychological status (i.e., mood, drowsiness, sedation) and cognitive function. Forty healthy West Virginia University (WVU) students will be allocated and randomized to receive: (1) 300 mg of pure CBD oil or (N=20) (2) placebo matched in appearance and taste (N=20). After consuming the study drug, each individual will participate in a 25–35-minute driving simulation, which includes a practice drive and brake reaction test, and their driving performance measured. To assess changes in psychological status (i.e., mood, drowsiness, sedation) and drug impairment-related cognitive function, the VAMS, SSS, DSST, TMT, PVT, SRT will also be administered to participants at baseline (prior to study drug consumption) and following completion of the driving simulation test. The primary outcome of this study will be driving performance, quantified using measures strongly associated with collision risk including number of lane departures, standard deviation of lateral position (i.e. weaving), reaction time, and collision occurrence. Secondary outcomes will be pre-post changes in well-validated measures of mood, drowsiness, mental sedation (VAMS, SSS) and cognitive function (DSST, TMT, PVT, SRT). We will also collect baseline demographic, health (including body mass index), and driving history data, including driving habits, along with data at the end of the survey to assess participant satisfaction and tests of

blinding. The entire protocol will be completed in one day and should take 4-4.5 hours to complete for each participant. We chose a parallel RCT design as opposed to a cross-over RCT to minimize participant burden, while still being able to study both within individual (i.e., test battery results) and between group effects (i.e., simulator and test battery performance).

**Study Population, Eligibility, Setting, and Recruitment.** Forty healthy adults will be recruited and randomized to receive either 300 mg of CBD (N=20) or placebo (N=20). The criteria for eligibility are as follows: 1) the participant must be currently enrolled as a WVU student, 2) be 18-30 years of age at time of study, 3) have a current drivers' license issued from any state in the United States, 4) has driven at least once in the past 30 days 5) is able to speak and read English, 6) is willing to be randomized and comply with study requirements including a urine drug test on the day they consent to participate in the experiment and complete a test drive to ensure the absence of simulation sickness, 7) not currently taking any daily prescription medications other than birth control, 8) have not been diagnosed with any serious chronic disease by a licensed healthcare provider (including but not limited to Alzheimer's and related dementias, Parkinson's disease or other neurodegenerative disorder, major depressive or anxiety disorder, schizophrenia or other serious mental illness, arrhythmias, cataracts, glaucoma, chronic obstructive pulmonary disease, diabetes, epilepsy, sleep apnea, and fibromyalgia), and 9) has an individual able to drive them home after testing or is willing to be driven home by study staff after testing completion.

Participants will be excluded if they 1) currently smoke or use tobacco products, 2) have used illegal drugs (including cocaine/crack, heroin, methamphetamine, 3,4-methylenedioxy-methamphetamine, inhalants, phencyclidine, lysergic acid, mushrooms, or marijuana) in the past 30 days, 3) has consumed CBD in the past 7 days, or 4) is currently pregnant or lactating. The health conditions and substances noted above have all been associated with changes in driving ability or performance. Also, limiting participants to those who are currently not using illegal drugs, tobacco products, and prescription medications may help minimize bias potentially caused by drug interactions with CBD or known impediments to driving performance from the medications themselves. Participants will be recruited from WVU. Email notifications about the study will be sent to the student body and flyers will be posted on boards throughout campus; this type of recruitment has been successful in other studies. The study will take place at the WVU Health Sciences Center.

**Consent, Screening, and Baseline Assessments.** Students who are interested in participating in the study will be contacted via study personnel. Participants will be given a brief overview of the study and its purpose and will be initially screened for eligibility using a standardized screening checklist. If the individual meets the inclusion and exclusion criteria, they will be invited to participate in the study. Participants will be given a list of instructions prior to their assessment. While participants should not be taking any routine prescription medications as part of the inclusion criteria, they will be told to abstain from taking any other types of medications including nutraceuticals, over-the-counter medications, vitamins, supplements 24 hours prior to coming to their appointment. Caffeine and alcohol should also not be consumed within 10 hours of their appointment. They will be instructed to get at least 6 hours of sleep the night prior and to only consume water prior to their scheduled visit.

At the research office, study personnel will explain the requirements, re-screen the participant, and review the consent form with each individual in a private room and obtain signed consent. After consenting, the participant will be asked to provide a urine sample which will be analyzed immediately onsite for potentially impairing or illicit drugs via a rapid urine test. If the individual tests positive for any potentially impairing substance, they will not be able to participate in the study. Anyone who tests positive for a drug will be referred to the Carruth Center on campus. If a participant's sample tests negative, they will then be allowed to practice on the driving simulator for approximately 10 minutes prior to engaging in any other study activities. This is necessary as some individuals who are prone to motion sickness may experience brief, mild nausea (e.g., simulator sickness). If there is evidence of simulator sickness, the individual will not be able to participate in the study, as they will likely not be able to complete the

protocol. Any reasons as to why an individual is not eligible to participate will be documented in a screening log. If no simulation sickness is observed, the student will then take the standardized and pilot-tested baseline survey regarding their demographics, health (including body mass index), and driving history along with the VAMS, SSS, TMT, DSST, PVT, and SRT tests.

These tests have all been deemed valid and reliable instruments and have been described in detail elsewhere. The tests will be administered by trained study personnel via a computer tablet and/or paper and pencil; personnel will then transfer the collected data to a secure, electronic database. Participants will also be given a standardized breakfast after baseline assessment.

**Allocation, Randomization and Blinding.** Participants will be randomized immediately after baseline assessments are completed to the CBD (N=20) or placebo group (N=20) using a sex-stratified 1:1 random block design to ensure equal distribution among treatment groups and sex. The participant and the PI will be unaware of group assignment (i.e. double-blind). [name], who will not have contact with participants, will generate a randomized assignment master list and provide sequentially numbered envelopes containing group assignment to the team member that helps consent participants. This team member will assign the unique number from the next envelope in sequence as the participant's study identification number and will record the participant's information in a secure, electronic master database.

**Intervention.** Protocol A consists of a 300 mg dosage of CBD oil which will be consumed orally. This dosage was chosen as it has been used in other studies consisting of both healthy and clinical populations and is well-tolerated with no major adverse events. CBD will be obtained from Zatural, a CBD manufacturer from Eden, Idaho. The CBD oil will be tested by Botanacor Laboratories (Denver, CO) for microbials, potency, heavy metals, trace THC, pesticides, and residual solvents to ensure purity, label accuracy, and safety; copies of laboratory reports will be maintained on premise. Protocol B is a placebo matched on appearance to the treatment (i.e., avocado oil potentially colored with food coloring). Both the CBD oil and placebo will be matched on taste (i.e., peppermint-flavored oil) prior to dispensing to each participant. After consumption of the respective protocol drug, the participant will be given a standardized meal and will then wait for 120 minutes to allow for digestion and for CBD to begin taking effect; this time frame was chosen based on the pharmacodynamics of CBD along with the consideration of participant burden (max absorption 2-5 hours). Next,

individuals will undergo a driving simulation and all participants will drive the same course. The simulator presents the individual with real life driving scenarios and is equipped with screens, a steering wheel, signals, and pedals (Figure 2). The participant will be instructed to drive the course for 25-35 minutes (this includes a practice drive and brake reaction time (BRT)). They will be instructed to follow normal driving rules, follow speed limits, and maintain constant speed and position within the lane, and brake when necessary. The simulation will include highway, suburban, rural, and urban driving scenarios which will incorporate turns, changes in speed, and avoidance of cars/pedestrians;

this course sequence and times were chosen to minimize simulator sickness. The simulator can monitor numerous aspects of drivers' performance and collect the data which is then downloaded and analyzed. Since we are investigating sedation and potential impairment, BRT, lateral position in the lane, lane departures, and collisions are the most telling performance measures. After the simulation, participants will retake the VAMS, SSS, TMT, DSST,

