### Target Population & Recruitment Methods

Our sample size is 40 individuals. We chose this number based on an a priori power analysis.

Our inclusion and exclusions criteria are as follows: 1) the participant must be currently enrolled as a WVU student, 2) be 18-30 years of age at time of study, 3) have a current drivers' license issued from any state in the United States, 4) has driven at least once in the past 30 days 5) is able to speak and read English, 6) is willing to be randomized and comply with study requirements including a urine drug test on the day they consent to participate in the experiment and complete a test drive to ensure the absence of simulation sickness, 7) not currently taking any daily prescription medications other than birth control, 8) have not been diagnosed with any serious chronic disease by a licensed healthcare provider (including but not limited to Alzheimer's and related dementias, Parkinson's disease or other neurodegenerative disorder, major depressive or anxiety disorder, schizophrenia or other serious mental illness, arrhythmias, cataracts, glaucoma, chronic obstructive pulmonary disease, diabetes, epilepsy, sleep apnea, and fibromyalgia), and 9) has an individual able to drive them home after testing or is willing to be driven home by study staff after testing completion.

Participants will be excluded if they 1) currently smoke or use tobacco products, 2) have used illegal drugs (including cocaine/crack, heroin, methamphetamine, 3,4-methylenedioxy-methamphetamine, inhalants, phencyclidine, lysergic acid, mushrooms, or marijuana) in the past 30 days, 3) has consumed CBD in the past 7 days, or 4) is currently pregnant or lactating. The health conditions and substances noted above have all been associated with changes in driving ability or performance. Also, limiting participants to those who are currently not using illegal drugs, tobacco products, and prescription medications may help minimize bias potentially caused by drug interactions with CBD or known impediments to driving performance from the medications themselves.

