[https://www.accessdata.fda.gov/drugsatfda\\_docs/label/2018/210365lbl.pdf](https://www.accessdata.fda.gov/drugsatfda_docs/label/2018/210365lbl.pdf)) and the United States Food and Drug Administration website (available at: <https://www.fda.gov/consumers/consumer-updates/what-you-need-know-and-what-were-working-find-out-about-products-containing-cannabis-or-cannabis>), several side effects of prescription CBD oil have been noted and could potentially harm participants. Prescription CBD oil can cause liver injury/hepatic dysfunction by elevating liver enzymes such as alanine aminotransferase [ALT] and/or aspartate aminotransferase [AST]). Prescription CBD oil can interact with other drugs or alcohol the participant may be taking potentially resulting in serious side effects. Mainly, using CBD oil with alcohol or other drugs, especially those used to treat anxiety, panic, stress, or sleep disorders, could slow brain activity, and increase the risk of sedation and/or drowsiness, which could lead to injury. Prescription CBD oil has also been shown to impact the gastrointestinal tract with side effects such as decreased appetite, diarrhea, weight loss, gastroenteritis, and abdominal pain/discomfort. Prescription CBD oil has also been shown to affect the nervous system and cause somnolence (drowsiness or sleepiness), lethargy, fatigue, malaise, insomnia, poor sleep quality, irritability, agitation, aggression, anger, drooling, or gait disturbances. Anti-epileptic drugs, such as prescription CBD oil, have been associated with suicidal behavior and/or suicide ideation. Prescription CBD oil has also caused hypersensitivity reactions, rashes, hypoxia, respiratory failure, and infection. Studies in animals exposed to CBD oil have also shown male reproductive toxicity, or damage to fertility in males or male off-spring of women who have been exposed to CBD oil. For this study, we are using 300 mg of CBD which is a relatively small dose. This dosage was chosen as it has been used in other studies consisting of both healthy and clinical populations and is generally well-tolerated with no major adverse events; most studies use 150-600 mg, while some have used >1,200 mg.

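### No written eligibility criterion covers known allergy or hypersensitivity, although the protocol lists hypersensitivity as a possible harm and gives every participant flavoured oil and two meals

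*Combined protocol and SAP*

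**What the plan says.** **Eligibility.** The criteria stand in the Research Summary, in Study Design & Methodology (the paragraph on population, eligibility, setting and recruitment) and in Target Population & Recruitment Methods. The exclusions are current tobacco use, illegal drug use in the past 30 days, and then "3) has consumed CBD in the past 7 days, or 4) is currently pregnant or lactating". The inclusion items nearest to allergy are number 7 (no daily prescription medication other than birth control) and number 8 (no diagnosed serious chronic disease, with a list of examples that is expressly not exhaustive). The main reason given for the health and substance items is that "The health conditions and substances noted above have all been associated with changes in driving ability or performance".

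**Entry rule.** Target Population & Recruitment Methods states that any student who meets these criteria may take part.

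**What participants are given.** The Intervention paragraph says: "Protocol B is a placebo matched on appearance to the treatment (i.e., avocado oil potentially colored with food coloring". It goes on: "Both the CBD oil and placebo will be matched on taste (i.e., peppermint-flavored oil) prior to dispensing to each participant". On food, the plan says that "Participants will also be given a standardized breakfast after baseline assessment", and a second standardized meal follows dosing.

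**Stated hazard.** The Risk & Benefit section says that "several side effects of prescription CBD oil have been noted and could potentially harm participants" and, within that list, that "Prescription CBD oil has also caused hypersensitivity reactions, rashes, hypoxia, respiratory failure, and infection".

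**The concern.** The protocol names hypersensitivity as something that could harm its participants, and it gives each of them several ingestible products. It does not use the entry criteria to keep out someone who already knows that they react to one of those products. These are healthy volunteers for whom the protocol states no direct benefit, so a risk that one question could remove is hard to justify. At stake is an avoidable reaction in either arm. The exposures differ by arm: CBD in one, avocado oil and possibly colouring in the other, and flavouring and meals in both.

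**Working it through.** No formula applies, and the plan gives no figure to reproduce. The check is a reading of the relevant sections against each other.

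1. **Count of criteria.** 9 inclusion + 4 exclusion = 13 items. In each of the three copies, 0 of 13 mention allergy or hypersensitivity to CBD, cannabis, avocado, peppermint, colouring or food. In the supplied text, the words allergy and allergic do not occur, and hypersensitivity occurs only in the Risk & Benefit section.

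2. **Exposure by arm.**

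| Item | Arm(s) | Participants |
|---|---|---|
| CBD oil | CBD | 20 |
| Avocado oil | Placebo | 20 |
| Food colouring (possible, not certain) | Placebo | up to 20 |
| Peppermint flavouring | Both | 40 |
| Standardized breakfast and post-dose meal | Both | 40 |

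3. **Could an existing criterion catch it?** Item 7 concerns daily prescription drugs, so an allergy managed by avoidance passes. Item 8 is open-ended and could be read to include a severe allergy diagnosed by a clinician. None of its named examples is an allergy, and a milder or undiagnosed one would not fall under it.

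4. **Could another screening step catch it?** The steps described after consent are a urine drug test and a practice drive to detect simulator sickness; neither detects allergy. The Protected Health Information section describes questions on chronic conditions, medication and illegal drugs, and does not mention allergy. The checklist and the health part of the baseline survey are mentioned, but their questions are not reproduced.

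5. **Could product testing or follow-up close the gap?** Laboratory testing is described for the CBD oil only and covers contaminants, potency and THC, not allergens. Physician availability and the follow-up contacts at 8-12 hours and about 24 hours come after exposure or do not act as a screen.

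6. **Entry rule applied.** Because meeting the criteria is sufficient, a student with a known allergy to, for example, avocado or peppermint meets the written conditions for entry.

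**The case against.** The strongest reply is that the working documents have not been seen. A checklist is used before the visit, eligibility is re-checked at the visit, a baseline survey covers health, and the consent pages are not in the text under review. Any of these may ask about allergy or list the ingredients. That stands. The supportable statement is that no written criterion excludes such a student. A reader might infer that an allergic student certainly would be dosed, but the documents do not establish that. The reply does not remove the gap, because the checklist is described as a screen for eligibility and eligibility has no allergy item.

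A second reply is that naming a risk does not oblige a protocol to carry a matching exclusion. The same section lists liver, gastrointestinal and other effects, most without their own criterion, and the hypersensitivity statement is about prescription CBD oil, not the nutraceutical used here. This also stands in part: the sections show a risk left unaddressed, not a contradiction. Even so, the protocol itself says those effects could harm participants. It also already uses eligibility to manage product risk, since the Research Summary excludes pregnant or lactating people for safety. For the same reason it would be wrong to say that the criteria concern driving alone.

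Third, the Risk & Benefit section does not discuss allergy to avocado oil, peppermint, colouring or food. That part of the concern rests on the ordinary observation that people can be allergic to things they eat.

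**Conclusion.** The concern holds in a limited form. No written criterion covers known allergy or hypersensitivity, and the entry rule makes the written criteria sufficient. All 40 participants are exposed to flavouring and meals, and 20 to each study oil. The conclusion assumes that the unseen checklist and consent form do not already deal with it; if they do, what remains is a mismatch between the criteria and those documents.

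Three stronger readings are not supported:

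- **A probability of harm.** The documents give no allergy prevalence. A figure built on an assumed one would describe the chance of enrolling an allergic student, not of a reaction.
- **Loss of the session and its data.** Nothing says that a reaction would end testing. Immediate stopping is described only for simulator sickness, and missing data are to be multiply imputed.
- **Colouring in both products.** It is mentioned only for the placebo, and only as a possibility.

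The point concerns participant safety. Sample size, power, alpha and the planned comparisons are unaffected.

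**What to change.** Add one exclusion item to all three copies of the criteria and to the existing screening checklist: self-reported known allergy or hypersensitivity to cannabis or CBD, or to any ingredient of the active oil, the placebo oil (including flavouring and any colouring) or the meals. The study physician should set the exact wording. If the checklist already asks this, bring the written criteria into line with it.

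The cost is an amendment submitted to the institutional review board and one more question at screening. No test, staff or analysis change is needed. The downside is that a few otherwise eligible students may be excluded.

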**Research Summary**

**Study Population** – Forty overall healthy adults will be recruited and randomized to receive either 300 mg of CBD (N=20) or placebo (N=20). The criteria for eligibility are as follows: 1) the participant must be currently enrolled as a WVU student, 2) be 18-30 years of age at time of study, 3) have a current drivers' license issued from any state in the United States, 4) has driven at least once in the past 30 days 5) is able to speak and read English, 6) is willing to be randomized and comply with study requirements including a urine drug test on the day they consent to participate in the experiment and complete a test drive to ensure the absence of simulation sickness, 7) not currently taking any daily prescription medications other than birth control, 8) have not been diagnosed with any serious chronic disease by a licensed healthcare provider (including but not limited to Alzheimer's and related dementias, Parkinson's disease or other neurodegenerative disorder, major depressive or anxiety disorder, schizophrenia or other serious mental illness, arrhythmias, cataracts, glaucoma, chronic obstructive pulmonary disease, diabetes, epilepsy, sleep apnea, and fibromyalgia), and 9) has an individual able to drive them home after testing or is willing to be driven home by study staff after testing completion.

Participants will be excluded if they 1) currently smoke or use tobacco products, 2) have used illegal drugs (including cocaine/crack, heroin, methamphetamine, 3,4-methylenedioxy-methamphetamine, inhalants, phencyclidine, lysergic acid, mushrooms, or marijuana) in the past 30 days, 3) has consumed CBD in the past 7 days, or 4) is currently pregnant or lactating. The health conditions and substances noted above have all been associated with changes in driving ability or performance. Also, limiting participants to those who are currently not using illegal drugs, tobacco products, and prescription medications may help minimize bias potentially caused by drug interactions with CBD or known impediments to driving performance from the medications themselves. Because the safety of CBD on fetuses or neonates is unknown, individuals who are pregnant or lactating are excluded for safety reasons.

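### Pregnancy is excluded for safety, but the screening described names no objective pregnancy check before dosing, although urine is already collected from every participant

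*Combined protocol and SAP*

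**What the plan says.** Exclusion criterion 4 removes anyone who "is currently pregnant or lactating". It appears in the Research Summary, in Study Design & Methodology, and in Target Population & Recruitment Methods. Only the Research Summary gives the reason: "Because the safety of CBD on fetuses or neonates is unknown, individuals who are pregnant or lactating are excluded for safety reasons". The Risk & Benefit section adds an animal reproductive finding, namely "damage to fertility in males or male off-spring of women who have been exposed to CBD oil".

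Screening is set out in Study Design & Methodology under Consent, Screening, and Baseline Assessments. Candidates are "initially screened for eligibility using a standardized screening checklist". At the office, "study personnel will explain the requirements, re-screen the participant, and review the consent form". After consent they are asked to "provide a urine sample which will be analyzed immediately onsite for potentially impairing or illicit drugs via a rapid urine test". The one consequence attached to that sample is this: "If the individual tests positive for any potentially impairing substance, they will not be able to participate in the study". Criterion 6 describes the same step when it requires willingness to "comply with study requirements including a urine drug test on the day they consent".

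A practice drive, the baseline tests, randomisation and dosing follow in that order. Criterion 7 lets participants use birth control, but nothing requires it.

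**The concern.** A checklist or a repeat screen can pick up a pregnancy that the participant knows about. Neither can pick up one that she does not know about. An exclusion meant to keep a fetus from being exposed to a substance of unknown fetal safety therefore has, as described, nothing behind it for the cases that questioning must miss. For recent illegal drug use, the plan adds an objective test to the screening questions. For pregnancy it describes none, although the same sample is in hand before dosing.

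What is at stake is participant safety and the enforcement of the protocol's own eligibility rule. The randomised comparison, the endpoints and the analysis are not affected.

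**Working it through.** The point rests on setting the provisions side by side. The plan has no figure here to reproduce.

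**Step 1: the rule and its reason.** Pregnancy is an exclusion in all three eligibility lists. The Research Summary states that the reason is safety.

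**Step 2: each screening step before dosing, and whether it can detect an unrecognised pregnancy.**

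| Step, in order | Purpose stated | Can it detect an unrecognised pregnancy? |
|---|---|---|
| Checklist at first contact | Eligibility | No |
| Repeat screen at the office | Eligibility | No |
| Consent | Agreement to take part | No |
| Urine sample | Impairing or illicit drugs | Not as described |
| Practice drive | Simulator sickness | No |
| Baseline survey and tests | Demographics, health, driving history, sedation and cognition | No pregnancy test named |

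No step, as described, would stop such a participant before randomisation.

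**Step 3: whether the situation can arise.** Participants are aged 18-30. Randomisation is stratified by sex, and Target Population & Recruitment Methods says that nobody is limited by gender, so women can enrol. Contraception is optional. Allocation is 1:1, so a participant who reaches randomisation has about an even chance of receiving CBD.

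**Step 4: scale.** The documents give neither the number of women nor a rate of unrecognised pregnancy, so both are assumed. Let n be the number of women on CBD and p the proportion with an unrecognised pregnancy among women who pass the other screens. With independence,

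P(at least one exposure) = 1 − (1 − p)^n.

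From the plan: 20 participants receive CBD. Assumed: n = 10 (an equal sex split), with n = 20 (all women) as the upper limit, and p from 0.1% to 2%.

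| p | n = 10 | n = 20 |
|---|---|---|
| 0.1% | 1 − 0.999^10 = 1.0% | 1 − 0.999^20 = 2.0% |
| 0.5% | 1 − 0.995^10 = 4.9% | 1 − 0.995^20 = 9.5% |
| 1% | 1 − 0.99^10 = 9.6% | 1 − 0.99^20 = 18.2% |
| 2% | 1 − 0.98^10 = 18.3% | 1 − 0.98^20 = 33.2% |

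The expected number of exposures with n = 10 is 10p, from 0.01 to 0.2. The result depends almost wholly on p, so the table gives an order of magnitude and is not an estimate.

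**The case against.** The strongest reply is that the documents do not say how pregnancy is ascertained. The content of the checklist and of the repeat screen is not given, the protocol overview is not shown, and the consent pages are not in the public text. A reader might infer that pregnancy is checked only by asking. That goes beyond the text: the Protected Health Information section lists chronic conditions, medication and illegal drugs among the things asked about, and does not mention pregnancy. This stands. The supportable statement is that the described screening names no objective check, and a test described elsewhere cannot be ruled out. Even then, the drug-only description of the urine test would need to be reconciled with it.

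Other objections also have weight:

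- Pregnancy is not singled out. No objective check is described for tobacco, recent CBD use, diagnosed disease or lactation either, and the stated reason for restricting drugs is bias in driving performance. This is true. But the exclusion for pregnancy and lactation is the one given an explicit safety reason, and a lactating participant knows that she is.
- The exposure is one 300 mg dose, which Risk & Benefit calls relatively small. The protocol nevertheless treats fetal safety as unknown and excludes on that ground. The point here is only that its rule should be enforced.
- A strip can miss the very earliest pregnancies, and the documents give no test sensitivity. The test would narrow the gap without closing it fully.
- A positive result is sensitive health information, while Confidentiality & Privacy promises minimal data collection. The referral route described covers only drug-positive results. This is a real cost and belongs in the fix.

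Two further inferences are not supported. A reader might conclude that the minimal-risk statement depends on this exclusion. Risk & Benefit instead discusses data security, simulator sickness and the CBD product, and the Research Summary points to legal status and tolerability. A reader might also take enrolling women to be a stated aim. The Background notes the lack of data in healthy females, but none of the three aims in Table 2 includes it, and stratification sets no number of women.

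**Conclusion.** The concern holds in this form: an exclusion made for safety has no objective check named before randomisation and dosing, so under the screening described a participant with an unrecognised pregnancy could be given CBD. This is more than a missing detail, because no checklist wording could detect a pregnancy that the participant is unaware of.

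With 10 women on CBD and a prevalence of 0.1% to 2%, the chance of at least one exposure is about 1% to 18%. Both inputs are assumptions, and the conclusion does not depend on them. It does depend on there being no test described only in the checklist, consent form or other material outside the public text.

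The change should be made. It is a participant-safety matter that can be closed cheaply, and it does not bear on the validity of the results.

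**What to change.** In Consent, Screening, and Baseline Assessments, add a rapid pregnancy test for female participants. Run it on the urine already collected and read it before the practice drive and randomisation. If it is positive, the existing exclusion applies; the exclusion itself does not change. Name the test beside the urine drug test in criterion 6, in all three eligibility lists, and in the consent form. If a test is already done under a document not made public, state it in these places and correct the drug-only description of the urine step.

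The cost is one strip per female participant tested: about 20 if half of the 40 enrolled are women (an assumption), plus any for screen failures. There may be an occasional extra screen failure. One more sensitive result has to be handled confidentially, with a private way to disclose it and a referral route, since the present referral text covers only drug-positive results. No extra sample or visit is needed, and the dose, design and analysis are unchanged.
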